7.2 EXCLUSION CRITERIA

Patients who have met all the above inclusion criteria listed in [Section 7.1](#) will be screened for the following exclusion criteria which are sorted and numbered in the following 4 subsections:

7.2.1 Exclusion criteria related to study methodology

- E 01. Any patient who, in the judgment of the Investigator, is likely to be noncompliant during the study, or unable to cooperate because of a language problem or poor mental development, or cannot be contacted in case of emergency.
- E 02. Patient who has taken other investigational drugs or SAR407899 for this study within 3 months or 5 half-lives from screening or randomization, whichever is longer.
- E 03. Any use of nitrates (except short-acting nitrates) and/or dipyridamole and/or PDE 5 inhibitors within one week prior to baseline PET scan or anticipated to be used during the study.
- E 04. Conditions/situations such as:
- Patients with a short life expectancy (including heart failure New York Heart Association [NYHA] III or IV).
 - Presence or history of drug hypersensitivity that in the opinion of the investigator would compromise patient's safety.
 - Any history or presence of clinically relevant pulmonary, gastrointestinal, hepatic, renal, metabolic, hematological, neurological, osteomuscular, articular, psychiatric, systemic, ocular, gynecologic (if female), or infectious disease, or signs of acute illness that according to Investigator's judgment, would adversely affect the patient's participation in the study.
- E 05. Esophageal dysmotility or esophagitis.
- E 06. Patients with acute coronary syndrome (ACS) (MI and/or unstable angina) in previous 3 months.
- E 07. Unsuccessful or incomplete coronary revascularization with residual obstructive stenosis or coronary artery disease progression in native vessels as documented on invasive coronary angiography ($\geq 50\%$ stenosis) within 24 months of enrollment.
- E 08. Percutaneous coronary intervention performed at the time of an ACS (MI or unstable angina) in the previous 12 months.
- E 09. Recent PCI within the past 3 months.
- E 10. Patients with history of coronary artery bypass grafting (CABG).
- E 11. Recent (≤ 3 months) major surgery (ie, valvular surgery, surgery for congenital heart disease), stroke, TIA, sustained ventricular arrhythmia, clinically significant structural heart disease (moderate-severe valvular disease, hypertrophic cardiomyopathy, congenital heart disease, pulmonary hypertension).

- E 12. Regional local flow abnormal perfusion defects at baseline PET scan*.
- *Note: if contemporary evidence with invasive coronary angiography or CCTA demonstrates non-obstructive coronary arteries or if the regional local flow abnormal perfusion defect on PET scan is consistent with previous studies then patient qualifies for the study.
- E 13. Patients with cardiac conduction abnormalities (second or third degree AV block, sick sinus syndrome, symptomatic bradycardia, sinus node disease) except in patients fitted with a functioning pacemaker.
- E 14. History or known carotid stenosis:
- Carotid stenosis (>50%)
 - or
 - History of carotid stenosis in patients with previous symptoms.
- E 15. Contraindication or known hypersensitivity to adenosine or regadenoson.
- E 16. Contraindication to aminophylline.
- E 17. Contraindication to vasodilator stress PET scan and/or CCTA if CCTA needed during screening.
- E 18. Inability to discontinue treatment with methylxanthines treatment within 24 hours prior to PET scan.
- E 19. Patient unable to read, understand and fill a questionnaire without any help (eg, partially visually impaired or blind).
- E 20. Blood donation (blood volume to be defined if needed depending on the country), any volume, within 2 months before inclusion (duration to be checked according to local regulations).
- E 21. Impossibility to meet specific protocol requirements.
- E 22. Patient is the Investigator or any Sub-investigator, research assistant, pharmacist, study coordinator, other staff or relative thereof directly involved in the conduct of the protocol.
- E 23. SBP <110 mmHg at baseline.
- E 24. Presence at baseline of **symptomatic** orthostatic hypotension (SBP decrease of 20 mmHg or more at Minute 3 or Minute 5 between seated and standing position), or **asymptomatic** orthostatic hypotension with a decrease in SBP equal or greater than 30 mmHg at Minute 3 or Minute 5 when changing from the seated to the standing position.
- E 25. Renal impairment with estimated glomerular filtration rate (eGFR) <50 mL/min/1.73 m² at screening and baseline.
- E 26. Male patient having a female partner of childbearing potential not protected by highly-effective method(s) of birth control (as defined in a local protocol amendment in case of specific local requirement).
- E 27. Women who are breast feeding.

E 28. Drug-induced liver injury related criteria:

- Underlying hepatobiliary disease.
- ALT >3 times the upper limit of normal (ULN).

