	
Contraception should be used during the whole study and for at least seven days corresponding to time needed to eliminate study treatment.
 
• Symptomatic stable angina pectoris (typical or atypical symptoms with an average of at least bi-weekly episodes over the past month),• Patients with non-obstructive (<50% stenosis) coronary arteries or intermediate stenosis (between 50 and 70%) should have fractional flow reserve (FFR) >0.80 or instantaneous wave-free ratio (iFR) >0.89 on angiogram documented within the previous 24 months*. In patients with stenting, a minimum diameter stenosis of <10% is required. 
or
 
Coronary computed tomography angiography (CCTA) with finding of non-obstructive coronary arteries within the past 24 months* in patients without previous PCI.
 
*Note: in cases of clinically suspected progression of atherosclerosis as per the Investigator, a more contemporary (ie, 6 months) evidence should be provided.
 
or
 
CCTA performed during screening period, with finding of non-obstructive coronary arteries, in patients diagnosed with MVA and stable angina without previous PCI who did not have a coronary angiogram or CCTA in the previous 24 months but between 24 months to 5 years.
 
• Baseline global CFR (measured during the study) assessed by ¹³N-ammonia or ⁸²Rubidium PET scan <2.0. 
Main Exclusion criteria:
 
• Esophageal dysmotility or esophagitis.• Any use of nitrates (except short-acting nitrates) and/or dipyridamole and/or phosphodiesterase type 5 (PDE5) inhibitors within one week prior to baseline PET scan or anticipated to be used during the study.• Patients with acute coronary syndrome (ACS) [myocardial infarction (MI) and/or unstable angina] in previous 3 months.• Unsuccessful or incomplete coronary revascularization with residual obstructive stenosis or coronary artery disease (CAD) progression in native vessels as documented on invasive coronary angiography (≥50% stenosis) within 24 months of enrollment.• Patients with history of coronary artery bypass grafting (CABG).• Percutaneous coronary intervention performed at the time of an ACS (MI or unstable angina) in the previous 12 months.• Recent PCI within the past 3 months.• Contraindication to vasodilator stress PET scan and/or CCTA if CCTA needed during screening.• Regional local flow abnormal perfusion defects at baseline PET scan*. 
*Note: if contemporary evidence with invasive coronary

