4.3 RATIONALE FOR THE STUDY

This study will evaluate SAR407899 compared with placebo in a population of patients with microvascular angina and/or persistent angina despite angiographically successful PCI (typical or atypical symptoms of angina pectoris), non-obstructive (<50% stenosis) coronary arteries on angiogram or intermediate stenosis with FFR >0.80 or iFR >0.89, and microvascular dysfunction documented by a global CFR <2.0 measured by PET. Angiographically successful balloon angioplasty with a reduction of a minimum stenosis diameter to <50% or for coronary stents a minimum diameter stenosis of <10%, with a final TIMI flow Grade 3 (visually assessed by angiography) without side branch loss, flow-limiting dissection, distal embolization, or angiographic thrombus.

This study will assess whether SAR407899 improves PET scan global CFR (25) before and after administration of a pharmacologic stressor (ie, vasodilator). Low CFR is considered as a hallmark of microvascular dysfunction. An improvement in CFR observed after interventions in this patient population would suggest an improvement in the underlying causal vascular biological abnormalities. Assessment of patient-reported outcome using the Seattle Angina Questionnaire physical limitation scale (SAQ-PL) due to its sensitivity will be used as secondary endpoint.

Change in angina episodes and short-acting nitrate intakes will be collected in the patient's diary.

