7 SELECTION OF PATIENTS

7.1 INCLUSION CRITERIA

- I 01. MVA and/or persistent stable angina despite angiographically successful PCI male or female patients with:
- A) Male and female patients not at childbearing potential ≥ 18 year-old or legal age of majority.
 - B) Female patient if she has undergone sterilization at least 3 months earlier or is postmenopausal.
 - Post-menopausal status is defined by having no menses for 12 months without an alternative medical cause,
 - In females not treated with HRT, menopausal status is confirmed by a high follicle stimulating hormone (FSH) level greater than 40 IU/L,
 - In females on HRT and whose menopausal status is in doubt (ie, in women aged less than 45 years), a highly effective contraception methods will be required. Contraception should be used during the whole study and for at least seven days corresponding to time needed to eliminate study treatment.
 - C) Symptomatic stable angina pectoris (typical or atypical symptoms with an average of at least bi-weekly episodes over the past month).
 - D) Patients with non-obstructive (<50% stenosis) coronary arteries or intermediate stenosis (between 50 and 70%) should have FFR >0.80 or iFR >0.89 on angiogram, documented within the previous 24 months*. In patients with stenting, a minimum diameter stenosis of <10% is required.
or
Coronary computed tomography angiography with finding of non-obstructive coronary arteries within the past 24 months* in patients without previous PCI.

*Note: in cases of clinically suspected progression of atherosclerosis as per the Investigator, a more contemporary (i.e., 6 months) evidence should be provided.
or
CCTA performed during screening period, with finding of non-obstructive coronary arteries, in patients diagnosed with MVA and stable angina without previous PCI who did not have a coronary angiogram or CCTA in the previous 24 months but between 24 months to 5 years .
 - E) Baseline global CFR (measured during the study) assessed by ^{13}N -ammonia or $^{82}\text{Rubidium}$ PET scan <2.0.
- I 02. Signed written informed consent.
- I 03. Not under any administrative or legal supervision.

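### Does exclusion E07 contradict inclusion I01 D for 50-70% lesions with FFR >0.80 or iFR >0.89?

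*Protocol*

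**What the plan says.** Protocol Section 7.1, I01 D, accepts two angiographic categories: non-obstructive arteries, below 50% stenosis, and lesions described as "intermediate stenosis (between 50 and 70%) should have FFR >0.80 or iFR >0.89 on angiogram, documented within the previous 24 months". The synopsis repeats this: "intermediate stenosis (between 50 and 70%) should have fractional flow reserve (FFR) >0.80 or instantaneous wave-free ratio (iFR) >0.89 on angiogram". A note to I01 D asks for evidence within 6 months, instead of 24, where the investigator clinically suspects that atherosclerosis has progressed. Section 4.3 describes the study population in similar terms, including "intermediate stenosis with FFR >0.80 or iFR >0.89, and microvascular dysfunction documented by a global CFR <2.0 measured by PET".

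Section 7.2.1, E07, excludes "Unsuccessful or incomplete coronary revascularization with residual obstructive stenosis or coronary artery disease progression in native vessels as documented on invasive coronary angiography". The threshold and window follow in the same sentence and also appear in the synopsis copy: "coronary artery disease (CAD) progression in native vessels as documented on invasive coronary angiography (≥50% stenosis) within 24 months of enrollment". E07 has no upper limit and no FFR or iFR condition.

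Section 7.2 sets the order of application. Its opening words, "Patients who have met all the above inclusion criteria listed in" Section 7.1, introduce the patients who are then screened against the exclusions.

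**The concern.** E07's threshold of 50% or more covers the whole of I01 D's 50-70% band. For a native lesion documented as progression, the FFR/iFR allowance therefore seems to admit nobody. The protocol does not say that this is intended. E12, in the same list, carries a note stating when a patient still qualifies ("if contemporary evidence with invasive coronary angiography or CCTA demonstrates non-obstructive coronary arteries" is one of its conditions), while E07 has no such note.

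The revascularisation part of E07 is also loose. It refers to residual obstructive stenosis without saying whether that is judged by percentage or by FFR/iFR, or whether the 50% bracket at the end of the sentence applies to it.

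At stake is consistent enrolment. With approximately 20 sites planned, one site might exclude a patient whom another would keep on the strength of a negative FFR or iFR. The enrolled population could then differ from the one described in Section 4.3.

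**Working it through.** No sample size, power or error-rate figure enters this question. The check sets the two criteria side by side.

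**Inputs**
- I01 D: below 50% accepted; 50-70% accepted if FFR >0.80 or iFR >0.89; angiogram within 24 months, or 6 months if progression is suspected.
- E07: native-vessel progression on invasive angiography at 50% or more, within 24 months; or unsuccessful or incomplete revascularisation with residual obstructive stenosis.
- Section 7.2: exclusions are applied after inclusions.
- Section 4.3, definition of successful PCI: "Angiographically successful balloon angioplasty with a reduction of a minimum stenosis diameter to" below 50%, or below 10% for stents.

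**Rule:** a patient passes these two criteria if I01 D is met and E07 is not triggered.

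**Cases**, assuming an invasive angiogram within the required window and FFR >0.80 or iFR >0.89:

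| Lesion | I01 D | E07 | Outcome |
|---|---|---|---|
| 1. Native, below 50% | met | not triggered | passes |
| 2. Native, 50-70%, no progression, no PCI | met | not triggered | passes |
| 3. Native, 50-70%, documented progression | met | triggered | excluded |
| 4. Untreated 50-70% lesion left after PCI | met | depends on the meaning of obstructive | unclear |
| 5. Above 70% | not met | not needed | fails |

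Treated segments raise no conflict, because Section 4.3 already requires less than 50% after balloon angioplasty or less than 10% after stenting.

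**Overlap in case 3.** The I01 D band spans 70 - 50 = 20 percentage points, and all 20 lie at or above E07's threshold: 20/20 = 100%. This measures overlap of definitions. It is not a share of patients, which the documents do not give.

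**Does E07 empty the intermediate category?** No. Case 2 passes, so the FFR/iFR allowance still has work to do. E07 takes a subset out of it, as any exclusion does.

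**A second reading of E07.** The sentence can be parsed so that both residual stenosis and native progression depend on unsuccessful or incomplete revascularisation. Case 3 would then arise only in previously revascularised patients. The overlap narrows but does not disappear.

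**Effect on the analysis.** Eligibility is settled before randomisation. Section 8.3 allocates 1:1, centrally, with stratification by PCI status, and the planned ANCOVA in Section 11.4.2.1 includes PCI status. Whichever way a site reads E07, the patients it enrols are allocated at random, so the reading cannot favour one arm. SAP Section 1.2 reports 10 of 78 planned patients randomised (10/78 = 12.8%), 8 of them with a post-baseline CFR. Its Table 1 replaces the model with descriptive tables and listings.

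**The case for a change.** The strongest case for a real defect rests on the I01 D note. It treats suspected progression as a reason for newer evidence and does not make it a bar to entry. If that newer evidence is an invasive angiogram showing progression to 60% with FFR 0.86, the document that satisfies I01 D is the one that triggers E07. An investigator could fairly ask which criterion governs, and no text states that excluding such patients is deliberate.

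Part of this stands. E07 would be clearer if it said how lesions with a negative FFR or iFR are handled and what obstructive means for a residual lesion.

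The rest carries less weight. The note fits with E07: suspicion prompts newer evidence, and E07 then acts on what that evidence shows. An exclusion need not state its rationale, and E12's note does not show that E07 needs one. Section 4.3 is a summary of the population, and many other exclusions also remove patients who match it. Divergence between sites is possible, but nothing in the documents shows that it occurred.

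**Conclusion.** The criteria can be applied together, and for documented native progression they give one outcome, exclusion. What remains is loose wording in E07 on residual lesions after PCI and on whether progression depends on prior revascularisation. Sites can fill that gap case by case without harm to the randomised comparison.

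The number of patients affected is unknown. There is no shown effect on bias, error rates or the primary analysis. That would have held with all 78 patients, and it holds for the descriptive analysis of the 10 randomised.

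The conclusion rests on two assumptions: that sites apply Section 7.2 in the order stated, and that eligibility is fixed before allocation, as Sections 8.3 and 10.1.2 provide. It takes no position on whether progressed or residual 50-70% lesions with a negative FFR or iFR ought to be eligible. If these criteria are reused, E07, I01 D with its note, Section 4.3 and the synopsis should be reconciled.

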7.2.2 Additional exclusion criteria during or at the end of screening before randomization

E 29. Patient who has withdrawn consent before randomization (starting from signed informed consent form).

8 STUDY TREATMENTS

8.1 INVESTIGATIONAL MEDICINAL PRODUCT(S) / NON INVESTIGATIONAL MEDICINAL PRODUCT(S)

8.1.1 INVESTIGATIONAL MEDICINAL PRODUCT(S)

Investigational medicinal products:

- SAR407899, 2.5 mg and 5 mg capsules.
- SAR407899 matching placebo.

Formulation: Capsules.

Route and method of administration: Oral administration, twice per day, in the morning and at bedtime, with or without a meal.

Dose regimen: 2 capsules in the morning and at bedtime. Dose may be taken with or without food as per preference of the patient.

Starting dose: [REDACTED].

[REDACTED]

- [REDACTED]
- [REDACTED]
- [REDACTED]
- [REDACTED]

Stopping criterion based on creatinine level:

- Stop study drug if creatinine level >150 µmol/L and increase from baseline >30%. In specific circumstances where creatinine blood level can be obtained only in the afternoon the day of the visit, the patient will be titrated according to titration scheme and if creatinine blood level meets stopping rules, the investigator will need to contact the patient before bedtime intake to permanently discontinue the study drug and schedule a premature study drug discontinuation visit.

[REDACTED]

When 19 patients will have completed first week of treatment, the DMC will review the clinical safety data. During the safety evaluation of the first 19 enrolled patients, these patients will continue to receive IMPs as per the titration schedule described above and enrolment will continue.

Dosing of SAR407899 is limited to 31 days.

8.1.2 NON INVESTIGATIONAL MEDICINAL PRODUCT(S)

The following classes of drugs are identified as non-investigational medicinal products (NIMP) because the medications are used to assess the primary endpoint of the study:

- PET radiopharmaceuticals (¹³N-ammonia and ⁸²Rubidium).
- Vasodilator stressors (adenosine and regadenoson).

The NIMPs should be used according to their approved labeling.

8.1.2.1 ¹³N-ammonia and ⁸²Rubidium

¹³N-ammonia and ⁸²Rubidium are PET radiopharmaceuticals. These NIMPs are administered to the patients to assess their primary endpoint using PET scan.

8.1.2.2 Adenosine and regadenoson

Adenosine and regadenoson are vasodilator stressors. These NIMPs are given to the patient to assess the primary endpoint using PET scan.

8.2 BLINDING PROCEDURES

8.2.1 Methods of blinding

For the double blind treatment package (DBTP), each double-blind SAR407899 treatment kit, either SAR407899 or placebo for SAR407899, will be prepared to contain 1 weekly (7 days +2 extra days) “child resistant” wallet of 36 capsules in each. In order to protect the blind, all SAR407899 double-blind treatment kit boxes (SAR407899 whatever the dose or Placebo for SAR407899) will have the same look and feel (identical capsules, same amount of capsules whatever the dose, packaging) and therefore will be labeled with a double-blind label.

8.2.2 Randomization code breaking during the study

In case of an adverse event (AE), the code should only be broken in circumstances when knowledge of the investigational medicinal product (IMP) is required for treating the patient.

If possible, a contact should be initiated with the Sponsor's monitoring team or medical expert before breaking the code.

Code breaking can be performed at any time by using the proper module of the interactive response technology (IRT) and/or by calling any other phone number provided by the Sponsor for that purpose. If the blind is broken, the Investigator should document the date, time of the day and the reason for code breaking.

If the code is broken, the patient must discontinue IMP administration but he/she continues the study.

Refer to [Section 10.5](#) for suspected unexpected serious adverse drug reaction requiring unblinding by the Sponsor.

8.3 METHOD OF ASSIGNING PATIENTS TO TREATMENT GROUP

At the screening visit, patients who will sign the informed consent form will be assigned an incremental subject number according to chronological order. The subject number remains unchanged during the study and allows the patient to be identified during the whole study. Stratification on the presence of angiographically successful PCI (YES/NO) will be performed.

The randomized treatment kit number list is generated centrally by Sanofi.

The IMPs are packaged in accordance with this list. The randomization and the treatment allocation (1:1) are performed centrally by an interactive voice/web response system (IVRS/IWRS). The IVRS/IWRS allocates treatment kits to the patient according to a prespecified randomization list, generated by the company in charge of the IVRS/IWRS.

A patient is considered as randomized as soon as the IVRS/IWRS has assigned a patient to active or placebo and indicated a treatment kit to be allocated to the patient, regardless whether the treatment kit was used or not (ie, patient registered by the IVRS/IWRS).

A patient cannot be randomized more than once in the study.

- All screening-failed patients will be entered in database with their subject number allocated at screening.

8.4 PACKAGING AND LABELING

For the double-blind treatment package (DBTP), each double-blind SAR407899 treatment kit, containing either SAR407899 or matching placebo, will be prepared to contain 1 weekly (7 days +2 extra days) "child resistant" wallets of 36 capsules in each.

In order to protect the blind, all SAR407899 double-blind treatment kit boxes (*SAR407899 whatever the dose or Placebo for SAR407899*) will have the same look and feel and therefore will be labeled with a double-blind label.

Packaging is in accordance with the administration schedule. One kit will be dispensed for first week of treatment. Then several kits will be dispensed according to the number of treatment weeks.

The content of the labeling is in accordance with the local regulatory specifications and requirements.

